## **8. INVESTIGATIONAL PRODUCT AND TREATMENT OF SUBJECTS**

### **8.1. Concomitant Medications**

All concomitant therapies (e.g., prescription and over-the-counter medications) taken by subjects from Baseline of Day 1 GC4419/placebo administration until 30 days following the last GC4419/placebo dose will be collected in the CRF. Additionally, any concomitant therapies if used to treat any serious or related AE will be recorded in the CRF.

If a subject withdraws consent for the study or is removed from the study completely (i.e., the subject is no longer participating in any study procedures or follow-up) no further data should be collected after the date of the subject's study discontinuation.

#### **8.1.1. Drug Interactions**

GC4419 is a strong inhibitor of CYP2D6.

Concomitant use of GC4419 increases the concentration of drugs that are CYP2D6 substrates, which may increase the risk of toxicities of these drugs. Concomitant use of GC4419 with CYP2D6 substrates where minimal increases in concentration of the CYP2D6 substrate should be avoided if possible in situations where minimal increases may lead to serious or life-threatening toxicities (substrates with a narrow therapeutic range). Such CYP2D6 substrates (Appendix 4) include certain antidepressants (eg, tricyclics), antipsychotics (eg, phenothiazines and most atypicals), and antiarrhythmics (eg, propafenone, flecainide).

Beta blockers that are CYP2D6 substrates (e.g. metoprolol) have been administered, with acceptable safety, concurrently with GC4419 to subjects in other clinical trials and may be administered in this study with careful monitoring of the subject.

In addition, concomitant use of GC4419 may decrease the concentration of active metabolites of prodrugs that require CYP2D6 for activation. Concomitant use of GC4419 with CYP2D6 prodrug substrates requiring functional CYP2D6 activity for their clinical benefit (eg, codeine, tramadol, taxomifen) may decrease their effectiveness.

Subjects should receive concomitant administration of a CYP2D6-substrate drug only if the investigator judges that doing so, and continuing blinded GC4419/placebo, is warranted in an individual subject's case.

See the Investigator's Brochure for additional information.

### **8.2. Prohibited Medications**

Investigators may prescribe any concomitant medication or supportive therapy deemed medically indicated for the care of the subject, with exception of the following prohibited medications/treatments:

- Nitrates, phosphodiesterase type 5 (PDE 5) inhibitors (e.g., sildenafil, tadalafil, or similar agents) or other concomitant drugs that in the judgment of the treating

investigator could create a risk of a precipitous decrease in blood pressure are prohibited until at least 24 hours after the last dose of blinded GC4419/placebo.

- Concurrent participation in a clinical trial of investigational therapy for SARS-CoV-2.
  - *Other approved or unapproved agents for SARS-CoV-2, including drug or biologic therapy including immunomodulatory treatments, administered on an expanded access, compassionate care, off-label, or emergency access basis may be administered. Use as part of another, concurrent clinical trial may be considered provided the site principal investigator determines that the mechanism of the other treatment is not expected to interfere with the mechanism of GC4419, and that completion of study requirements for this protocol will not be compromised.*
  - *Examples of acceptable concurrent medications under this provision include remdesivir, hydroxychloroquine (alone or with azithromycin) or convalescent plasma, and other drug or biologic treatments for SARS-CoV-2 as long as not part of a clinical trial other than the present trial.*

Subjects who receive prohibited medications will not automatically be removed from the study; however, administration of a prohibited medication is a significant deviation from the protocol and must be reported to the Medical Monitor as soon as possible and the presiding IRB/IEC/REB (per institutional guidelines). The decision for study continuation or discontinuation will be made at that time on a case-by-case basis and in consideration of the clinical requirement and circumstances.

### **8.3. Description of Study Drug GC4419**

GC4419 is formulated as a sterile solution at the following concentration:

- 99 mg avasopasem manganese in 11mL: 9 mg/mL in 26 mM sodium bicarbonate-buffered 0.9 wt. percentage saline for parenteral administration .

#### **8.3.1. GC4419 Drug Packaging and Labeling**

Open-label GC4419 will be provided as single-use vials for daily doses to be administered IV.

GC4419 is packaged as an  $11\text{ mL} \pm 0.1\text{ mL}$  aliquot in a 10 mL glass vial of which 10 mL be added into 170 mL of normal saline, for daily IV administration over 180 minutes. Each bottle will be labeled with the appropriate language, including information required by local health authority regulations.

Further label details will be provided in a separate Pharmacy Manual.

#### **8.3.2. Placebo Packaging and Labeling**

Placebo will be normal saline for parenteral administration only and is to be provided by investigative site.

### **8.3.3. Study Drug Storage**

GC4419 should be stored in a blinded fashion and refrigerated at 2°C-8°C in a secured and controlled area with restricted access. Temperature excursions above freezing and up to 25°C or down to 0.1°C for four hours are accepted; however, the Sponsor, or its designee must be notified immediately of the temperature excursion to ensure proper oversight.

Once prepared, the IV bags containing GC4419/placebo mixtures must also be stored at 2°C to 8°C until use and must be administered to subjects within 24 hours of preparation. GC4419 dosing solutions must not be frozen at any time. If freezing of the material is evident, that supply must be quarantined per institutional guidelines and Galera Therapeutics, Inc. or its designee must be notified immediately.

### **8.3.4. Study Drug Preparation**

GC4419 will be provided to the study site in single use, sterile, pyrogen-free vials ready for dose preparation. Proper mixing with normal saline is required. Standard aseptic techniques will be used to maintain sterility. Infusions should be prepared using a sterile 0.22 micron syringe filter prior to introduction into the infusion bag.

To prepare IV solutions, investigational pharmacists will extract 10 mL GC4419 from a single vial and add to 170 mL of normal saline. No additional modifications or adjustments are to be made to the infusion solution.

To prepare placebo solution, sites are to prepare 180 mL of normal saline.

IV bags should be prepared and labelled in a blinded manner.

Further information and preparation details will be provided in a separate Pharmacy Manual.

### **8.3.5. Administration**

Prepared GC4419/placebo will be administered intravenously at an infusion rate that totals 180 min ( $\pm$  6 min to account for saline overfill) for the total dose assigned. Infusions of GC4419/placebo must be administered using an infusion pump (i.e., not by drip rate). Infusion pump models are not specified and may be per institutional preference/standard.

To facilitate administration of GC4419/placebo according to the study schedule, an indwelling venous access device may be used, at the discretion of the treating Investigator. If port is to be used for other medications, a flush is required prior to GC4419/placebo administration, at minimum.

### **8.3.6. Accountability and Compliance**

Compliance with GC4419/placebo dosing, including administration details (e.g., volume, start, stop times, etc.) should be documented in the source documents and recorded on the CRF.

The Investigator is responsible for ensuring adequate accountability of all used and unused GC4419. This includes acknowledgment of receipt of each shipment of GC4419 (quantity and condition), subject dispensing records, and quantity of GC4419 vials returned or destroyed.

Dispensing records will document quantities received from the Sponsor and quantities dispensed to subjects, including container number or lot number, date dispensed, subject identifier number, subject initials, and the initials of the person dispensing the medication. Any GC4419 that is prepared but not used must also be recorded in the dispensing records.

All GC4419 supplies and associated documentation will be reviewed and verified by an unblinded study monitor. All GC4419 and used containers are to be retained by the site until notified by the unblinded study monitor, who will instruct the site in the disposal and/or destruction of all used GC4419 supplies. Copies of all forms, documenting drug receipt at the study site, drug transportation to satellite sites, and drug return to the Sponsor, together with drug accountability records, will be retained according to the regulations governing record retention.

The Investigator will not allow GC4419 to be given to any patient not included in the study or to any unauthorized person.

### **8.3.7. Study Drug Handling and Disposal**

After completion of the study, all unused study drug will be inventoried and if possible, destroyed locally at the site. GC4419 should not be returned directly to Galera Therapeutics, Inc. unless specifically requested by Galera Therapeutics, Inc.. The study monitor will instruct the site in the disposal and/or destruction of all used and unused GC4419 supplies. Destruction of any GC4419 should be documented appropriately.

## **9. TOXICITY MANAGEMENT**

### **9.1. Anticipated toxicities of GC4419**

Based on the drug's mechanism of action, adverse effects anticipated with GC4419 are attributable to transient potentiation of nitric oxide. Clinical results with GC4419 to date are consistent with this. These effects have been IV infusion related and transient, typically with onset during or at the end of infusion, resolving within 1-2 hours of cessation of GC4419 administration. At the dose and schedule planned in this trial, these effects may include mild hypotension, postural lightheadedness/presyncope, and perioral/facial tingling or paresthesia. Mild nausea and vomiting have also been observed in human subjects receiving GC4419.

See the investigator's brochure for additional details.

### **9.2. Dose Delays and Dose Modifications for Toxicity**

*For any given subject, study drug infusions should not begin if the subject's mean arterial pressure (MAP) is less than 65 mmHg.*

For any given subject, hold blinded GC4419/placebo and reduce by 25% (from the initial dose) for all future infusions if:

- During infusion or within 1 hour of completing infusion, the subject experiences an acute decrease in systolic blood pressure requiring bolus fluid resuscitation OR requiring initiation of vasopressor therapy OR increased vasopressor therapy. Hold GC4419/placebo until the dose of vasopressor therapy is stable and bolus fluid resuscitation is not required.
- The subject develops serum creatinine  $> 5$  mg/dL. Hold GC4419/placebo until the creatinine is  $=< 5$  mg/dL.
- The subject develops serum total bilirubin  $> 6$  mg/dL, or AST or ALT  $> 10$  times upper limit of normal. Hold GC4419/placebo until the parameters in question are below these levels.
- The subject experiences a serious or severe adverse event considered by the investigator to be related or possibly related to blinded GC4419/placebo. Hold GC4419/placebo until the event is no longer serious or severe.

Up to two such dose reductions for a cumulative 50% from the initial dose of GC4419/placebo will be permitted for a given subject. If a subject cannot tolerate GC4419/placebo infusion after a 50% dose reduction, all dosing with GC4419/placebo for that subject will be discontinued.

Patients unable to tolerate GC4419/placebo must discontinue treatment with GC4419/placebo but should continue with other protocol assessments at the discretion of the treating investigator and with the ongoing consent of the subject.

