### **Safety Monitoring and Toxicity Management:**

Adverse/Serious Adverse Event assessments per GCP standards. Severity of events will be graded according to the NCI-CTCAE v 5.0.

*For any given subject, study drug infusions should not begin if the subject's mean arterial pressure (MAP) is less than 65 mmHg.*

For any given subject, hold blinded GC4419/placebo and reduce by 25% (from the initial dose) for all future infusions if:

- During infusion or within 1 hour of completing infusion, the subject experiences an acute decrease in systolic blood pressure requiring bolus fluid resuscitation OR requiring initiation of vasopressor therapy OR increased vasopressor therapy. Hold GC4419/placebo until the dose of vasopressor therapy is stable and bolus fluid resuscitation is not required.
- The subject develops serum creatinine > 5 mg/dL. Hold GC4419/placebo until the creatinine is = < 5 mg/dL.
- The subject develops serum total bilirubin > 6 mg/dL, or AST or ALT > 10 times upper limit of normal. Hold GC4419/placebo until the parameters in question are below these levels.
- The subject experiences a serious or severe adverse event considered by the investigator to be related or possibly related to blinded GC4419/placebo. Hold GC4419/placebo until the event is no longer serious or severe.

Up to two such dose reductions for a cumulative 50% from the initial dose of GC4419/placebo will be permitted for a given subject. If a subject cannot tolerate GC4419/placebo infusion after a 50% dose reduction, all dosing with GC4419/placebo for that subject will be discontinued.

Patients unable to tolerate GC4419/placebo must discontinue treatment with GC4419/placebo but should continue with other protocol assessments at the discretion of the treating investigator and with the ongoing consent of the subject.

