### 5.2. Secondary Objectives

The following secondary objectives will be assessed through a 28-day period to align with the primary objective:

- To assess the safety of avasopasem in the study population
- To evaluate the frequency of successful ventilator weaning
- To evaluate the number of days alive and intensive care-free
- To evaluate the number of days alive and ventilator-free
- To evaluate the number of days of minimum SpO2/FIO2 ratio or PaO2/FIO2 > 300
- To evaluate the number of days alive without vasopressor/catecholamine support
- To evaluate the incidence of mean arterial pressure < 65 mmHg on optimized vasopressor therapy
- To evaluate the number of days alive with a SOFA score of 6 or less
- To evaluate the percentage of subjects with an increase in mean arterial pressure of 10 mm Hg or more at the end of more than one infusion of GC4419

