### **7.5. Subject Withdrawal Criteria**

In accordance with the Declaration of Helsinki, a subject has the right to withdraw from the study at any time for any reason. The Investigator may also, at his/her discretion, discontinue a subject from participating in this study at any time. Additionally, study treatment may be discontinued for any of the following reasons:

- AE
- Medical requirement to administer a contra-indicated medication
- Subject non-compliance
- Subject has a confirmed positive serum pregnancy test
- Discontinuation of the study at the request of the Sponsor

The primary reason for ceasing treatment will be clearly documented in the subject's medical record and recorded on the appropriate CRF page. A subject who permanently discontinues treatment with GC4419/placebo will not be allowed to be retreated.

If a subject discontinues study drug as a result of an AE or serious adverse event (SAE), every attempt should be made to keep the subject in the study and continue to perform the required

study-related follow-up and procedures. If this is not possible or acceptable to the subject, the subject may be withdrawn from the study.

If a subject withdraws consent, additional details about the reasons for that decision will be sought and documented.

Withdrawn subjects will not be replaced.

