## **10. ASSESSMENTS**

The study procedures to be conducted for each patient enrolled in the study are presented in [Appendix 1](#).

Any deviation from protocol procedures should be documented and explained in the source documents. The sponsor (or designee) and the site's IRB (as required by the IRB's policies and procedures) should be notified as soon as possible of any substantial deviations potentially affecting patient safety, study drug administration or the assessment of safety, efficacy, and tolerability parameters.

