### **10.3. ADVERSE EVENTS AND SERIOUS ADVERSE EVENTS**

Adverse Events and Serious Adverse Events will be assessed daily during hospitalization and weekly after hospital discharge, for a total of 6 weeks after day 1 and encompassing at least 30 days after end of GC4419/placebo dosing (experimental arm subjects). Post-treatment AE assessments may be done on an outpatient basis for subjects who are discharged from the hospital.

The investigator is responsible for the detection and documentation of events meeting the criteria and definition of an AE or SAE as provided in this protocol. Throughout the study, AEs will be recorded in the source documents and on the appropriate pages of the CRF regardless of whether the AEs are considered related to GC4419/placebo. To avoid confusion, the AE should be recorded in standard medical terminology.

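### Section 9.2 makes assessments after stopping for intolerance discretionary, in conflict with Sections 7.5 and 10, so 28-day secondary data other than AE/SAE reports can be lost selectively

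*Combined protocol and SAP*

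**What the plan says.** Four places in the protocol bear on what happens after a subject stops study drug.

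- **Section 9.2** (dose modifications) requires intolerant subjects to stop study drug. On what happens next, its wording is: "should continue with other protocol assessments at the discretion of the treating investigator and with the ongoing consent of the subject". The synopsis, under Safety Monitoring and Toxicity Management, repeats this: "should continue with other protocol assessments at the discretion of the treating investigator".
- **Section 7.5** (withdrawal) sets a duty for stops brought about by adverse events, serious or not: "every attempt should be made to keep the subject in the study and continue to perform the required". What that sentence asks sites to carry on with is the follow-up schedule. It then allows an exit: "If this is not possible or acceptable to the subject, the subject may be withdrawn from the study". The same section says: "The Investigator may also, at his/her discretion, discontinue a subject from participating in this study at any time".
- **Section 10** is general, points to Appendix 1 and makes no exception for subjects off drug. Its opening words are: "The study procedures to be conducted for each patient enrolled in the study are presented in".
- **Section 10.3** covers adverse events without a discretion clause, with Day 1 as the starting point: "Adverse Events and Serious Adverse Events will be assessed daily during hospitalization and weekly after hospital discharge, for a total of 6 weeks". Sections 10.5.2 and 10.8 add 30 days of follow-up after treatment, with SAEs followed to resolution or a new baseline.

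On the window, Section 5.2 states: "The following secondary objectives will be assessed through a 28-day period to align with the primary objective". Section 11.4 keeps every randomized and dosed subject in the analysis, and Section 11.7.2 makes the secondary analyses descriptive. Section 8.1 bars further data collection once a subject is removed from the study completely.

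**The concern.** A site dealing with an intolerant subject will open Section 9.2, and there it finds that further assessments are a matter of judgement. Section 7.5 asks for every effort, and Section 10 applies the full schedule. The protocol does not say which instruction prevails.

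The subjects concerned are not a random subset. Section 9.1 names mild hypotension as an anticipated effect of GC4419. The first hold-and-reduce trigger in Section 9.2 is an acute pressure fall, during or soon after infusion, that needs fluid or vasopressor support. Repeated events of that kind can lead to discontinuation, so stopping may be more frequent on GC4419 even though the trial is blinded. Those who stop may also be the sicker subjects. Vasopressor-free days and MAP below 65 mmHg on optimized vasopressors are themselves secondary endpoints, so the data at risk lie close to the reason for stopping.

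With 25 subjects per arm, a few missing courses can change how a days-free summary reads. Data that were never recorded cannot be restored at analysis.

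**Working it through.** **1. Which data are exposed.** Section 11.5.2 lists nine secondary endpoints.

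- Seven depend on status recorded after a stop: weaning, ICU-free days, ventilator-free days, oxygenation days, vasopressor-free days, MAP below 65 mmHg, and SOFA of 6 or less.
- The eighth, safety, is exposed only for laboratory values and vital signs, because Sections 10.3, 10.5.2 and 10.8 secure AE and SAE collection.
- The ninth, a MAP rise at the end of more than one infusion, is tied to infusions and cannot be collected once they cease.

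**2. How much of the window.** Dosing lasts 7 days (Section 6.2) and the endpoints run 28 days, so at least 28 − 7 = 21 days follow any stop. Not all of those days carry every daily item. In the Appendix 1 table as extracted, the ventilation and SOFA rows are blank after ICU discharge.

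**3. Illustrative size on a days-free mean.** The documents give no stopping rate and no expected number of free days. Assumptions:

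- The true mean is 8 of 28 days in both arms.
- k of 25 GC4419 subjects and no placebo subjects are lost. The upper value of 5 is 20% of 25, which does not exceed the more-than-20% DMC limit in Section 14.4.
- Lost subjects have true mean m and drop out of the summary.

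Observed mean = (25 × 8 − k × m)/(25 − k), so the shift is k(8 − m)/(25 − k).

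| Lost (k) | m = 0 | m = 4 | m = 8 |
|---|---|---|---|
| 1 | 8/24 = +0.33 | 4/24 = +0.17 | 0 |
| 3 | 24/22 = +1.09 | 12/22 = +0.55 | 0 |
| 5 | 40/20 = +2.00 | 20/20 = +1.00 | 0 |

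**4. Direction.** Suppose instead that unrecorded days count as not free and, at the extreme, all of a lost subject's free days fall after the stop. The shift is then −k × m/25. For k = 5 and m = 4 it is −20/25 = −0.8 days, which goes against GC4419. The sign therefore depends on a missing-data rule. The protocol text gives none for these endpoints, and Section 11.1 leaves technical detail to a separate SAP.

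**5. Primary endpoint and power.** The planned size reproduces. For 50% versus 90% survival, two-sided 0.05 and 80% power, the uncorrected formula gives [1.96√(2 × 0.7 × 0.3) + 0.842√(0.25 + 0.09)]²/0.4² = 19.4. The continuity correction, (19.4/4) × [1 + √(1 + 4/(19.4 × 0.4))]², gives about 24.1, so 25 per arm.

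If five GC4419 subjects were also missing for mortality, unstratified Fisher exact power would move only from 83.3% (25 vs 25) to 81.5% (25 vs 20). The issue is bias, not power.

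That mortality bias would need vital status to be lost as well. With true mortality of 50% in both arms and mortality q among those lost, observed GC4419 mortality is (12.5 − k × q)/(25 − k). For k = 1, q = 0.6 it is 11.9/24 = 49.6%. For k = 5, q = 1 it is 7.5/20 = 37.5%. The spurious benefit would be 0.4 to 12.5 points.

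**The case against.** The case for calling this minor is that Section 9.2 starts from continuing, with discretion only as a qualifier. Section 10 applies Appendix 1 to everyone, Section 9.3 says ventilator settings will be collected on schedule, and Section 12.3 classes a missed procedure as a deviation. Investigators are blinded, and the secondary endpoints are descriptive. All of this is correct. It shows that other sections point towards collection, but it does not remove the permission in Section 9.2 and the synopsis.

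Several stronger readings are tempting, and the documents do not support them:

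- **That Section 7.5 requires the assessments.** It is a best-effort instruction with an exit and its own investigator discretion.
- **That the events listed in Section 9.2 are stopping triggers.** They are hold-and-reduce triggers. Discontinuation under that section follows only if the subject cannot tolerate infusion after the permitted reductions, so the group is narrower than the list suggests.
- **That stops for other reasons carry no follow-up duty.** Section 7.5 has no specific instruction for a contra-indicated medication or non-compliance, nor for the renal replacement rule in the synopsis. Sections 10 and 10.3 still apply by default.
- **That the safety comparison as a whole is lost.** AE and SAE collection is secured separately.
- **That mortality is left to discretion.** Death is an SAE under Section 10.4.2 and falls within the Section 10.3 window. Vital status is at risk only through complete withdrawal from the study (Sections 7.5 and 8.1).

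**Conclusion.** The conflict is real and appears in both the synopsis and the body. As written, the protocol permits outcome-related loss of daily ventilation, oxygenation, vasopressor, MAP, SOFA and laboratory data after discontinuation for intolerance. This can bias the 28-day secondary endpoints.

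A reader might infer that every days-free count will favour GC4419. The documents do not support that. The direction depends on how missing days are scored and on whether those who stop differ from the rest. The size rests on assumed figures: 0 to about 2 days on a days-free mean if 1 to 5 of 25 GC4419 subjects drop out of the summary, the true mean is 8 days in both arms, and no placebo subject is lost. If those lost do not differ from the others, the shift under that exclusion is zero.

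The point is worth correcting because the remedy is simple and the loss cannot be repaired afterwards. It does not undermine the primary analysis.

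**What to change.** These changes concern data collection only and leave every hold, reduction and discontinuation rule as it stands.

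1. In the synopsis and Section 9.2, delete the clause that leaves continued assessments to the investigator's discretion.
2. In Section 7.5, extend the follow-up duty from stops caused by an AE or SAE to stops of study drug for any reason.
3. Add: *Stopping study drug does not end follow-up. Vital status and the Appendix 1 assessments not tied to an infusion continue through Day 28, and adverse event follow-up continues as in Section 10.3, unless consent for follow-up is withdrawn or another section requires withdrawal from the study.*
4. Reconcile this with the Section 7.5 sentence that lets the investigator end participation, since Section 8.1 then stops all data collection.

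The carve-outs in item 3 are needed. Infusion-timed pressures, pharmacokinetic samples and drug administration cannot continue off drug, and Section 10.10 requires withdrawal of a subject who becomes pregnant. The SAP should also state how missing days are scored in each days-free endpoint.

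The cost is the wording edits and a small amount of extra data collection on the existing schedule. No new procedure is added, and Appendix 1 already allows follow-up by telephone or virtual visit when a subject cannot attend in person.
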